## 5. GENERAL METHODOLOGY AND CONVENTIONS

### 5.1. Hypotheses and Decision Rules

The treatment comparison being made in this study is zavegepant 10 mg versus placebo. The null and alternative hypotheses are shown below. The test will be 2-sided.

The null hypothesis ( $H_0$ ) is that the difference in the stratified response rate between treatment groups is zero.

The alternative hypothesis ( $H_1$ ) is that the difference in the stratified response rate between treatment groups is not zero.

Type I error is controlled by a hierarchical gate-keeping procedure. First, the family of 2 co-primary endpoints is tested. In particular, zavegepant is tested for superiority against placebo at a 2-sided  $\alpha=0.05$  level for both co-primary endpoints. If the tests of both co-primary endpoints are significant (ie, both p-values are  $\leq 0.05$ ), then the key secondary endpoints are tested hierarchically at the 2-sided  $\alpha=0.05$  level in the order shown in Section 3.2.1. Thus, a key secondary endpoint is tested only if the preceding key secondary endpoint in the hierarchy is determined to be significant (ie, p-value  $\leq 0.05$ ). If a test in the hierarchy is not significant, then any further tests on endpoints in the sequence will have p-values presented only for descriptive purposes, and no conclusions are drawn from those results.

For other secondary endpoints and exploratory endpoints, no attempt is made to adjust for multiplicity. Any other secondary endpoints and exploratory endpoints for which p-values are produced are evaluated at an unadjusted, 2-sided  $\alpha=0.05$  level and presented only for descriptive purposes.

## 5.2. General Methods

### 5.2.1. Analyses for Continuous Endpoints

Continuous variables will be summarized using summary statistics (e.g., n, mean, median, standard deviation (SD), minimum, and maximum).

### 5.2.2. Analyses for Categorical Endpoints

Categorical variables will be summarized as the number and percentage of participants within each category. Percentages in frequency tables are calculated against the number of participants in each treatment group in the specified analysis set. For each endpoint, Mantel-Haenszel risk estimation will be used for the difference in percentages of participants achieving the endpoint response criteria (zavegepant-placebo) stratified by country/region. The difference in percentages between treatment groups will be presented with p-value and asymptotic standard error (ASE) together with a 95% CI based on normal approximation. For individual treatment group, the percentage of participants achieving the endpoint response criteria will be presented with ASE and a 95% CI based on normal approximation.

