#### 9.3.1. General Considerations

Descriptive statistics for all efficacy and safety endpoints at appropriate time points will be provided by treatment group. Continuous variables will be summarized by standard descriptive statistics (n, mean, standard deviation, median, minimum and maximum), and categorical variables will be summarized by the number and percentage in each category (with the corresponding sample size).

In treatment comparisons of binary endpoints, a stratified CMH test will be used, and CIs will be based on a normal approximation to the binomial distribution.

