### 9.5. Sample Size Determination

It is anticipated that about 90% of the 700 participants randomized to each treatment group will have a headache in the allotted time period, resulting in approximately 630 participants evaluable for efficacy in each treatment group.

The sample size calculation is based on pooled efficacy results from the Phase 2/3 BHV3500-201 and Phase 3 study BHV3500-301. The response rates for zavegepant 10 mg and for the placebo group in pooled analysis were 23.2% and 15.1%, respectively, for pain freedom at 2 hours postdose, and 40.5% and 32.1%, respectively, for MBS freedom at 2 hours postdose.

A target sample size of 1260 evaluable participants (630 per group) will provide approximately 95.7% power for the co-primary endpoint of pain freedom at 2 hours postdose, approximately 87.5% power for the co-primary endpoint of MBS freedom at 2 hours postdose, and approximately 84% power to detect a difference between treatment groups for both endpoints jointly, using a 2-sided alpha of 0.05.

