### 6.3. Exploratory Endpoints

#### 6.3.1. Percentage of participants with a pain intensity of none at 15 minutes, 30 minutes, 45 minutes, 60 minutes, 90 minutes, 2 hours, 3 hours, 4 hours, 6 hours, 8 hours, 24 hours, and 48 hours postdose

##### 6.3.1.1. Main Analysis

- Estimand strategy: Composite policy ([Section 2.2.3](#))
- Analysis set: EAS ([Section 4](#)).
- Analysis methodology: The Mantel-Haenszel risk estimation stratified by country/region will be used. See details in [Section 5.2.2](#).
- Intercurrent events and missing data: (1) Taking rescue medication at or before each of the assessed time points postdose (RM=F; see [Appendix 2.1](#)) and (2) missing pain intensity at each of the assessed time points postdose respectively (NC=F; see [Section 5.3](#) for definition) will be regarded as failures.

Treatment group comparisons of the percentage of participants with pain freedom at each time point from 15 minutes through 48 hours postdose (i.e., in the 15-minute to 48 hours postdose analysis window) will present similar statistics as the main analysis of the co-primary endpoint of pain freedom (see [Section 6.1.1.1](#)).

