#### 6.4. Subset Analyses

For the co-primary and key secondary endpoints, subgroup analyses will be conducted for the following baseline demographic and characteristic variables:

- Country/region at randomization: China, Korea, Taiwan
- Age at informed consent category 1: <40, ≥ 40

- Sex: male, female
- BMI category:  $<25 \text{ kg/m}^2$ ,  $\geq 25$  to  $<30 \text{ kg/m}^2$ ,  $\geq 30 \text{ kg/m}^2$
- Aura on study before dosing: yes, no
- History of migraine with aura: yes, no (see Section 6.5.1.2)
- Historical number of moderate to severe migraine attacks per month:  $<4$ ,  $\geq 4$  (overall median)
- Stable prophylactic migraine medication use through randomization: yes, no.

For the primary endpoint of “percentage of participants with an MBS reported before dosing that is absent at 2 hours postdose”, the following characteristic variables will additionally be used for subgroup analysis:

- MBS on study before dosing: Nausea
- MBS on study before dosing: Phonophobia
- MBS on study before dosing: Photophobia

Main analysis method described in Section 5.2.2 will be used, except for the subgroup analysis by country/region at randomization, in which Mantel-Haenszel risk estimation without stratification will be conducted.

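### The normal-approximation 95% CI prescribed for every per-arm response rate breaks down when responders are few, and SAP 5.2.2 has no rule for sparse cells

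*SAP*

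**What the plan says.** SAP 5.2.2 sets one method for all binary endpoints. For each arm, the response percentage "will be presented with ASE and a 95% CI based on normal approximation". For the treatment effect it sets a Mantel-Haenszel difference stratified by country/region, with its own standard error, normal-approximation CI and p-value. Protocol 9.3.1 agrees: "CIs will be based on a normal approximation to the binomial distribution". Protocol 9.3.2.1 repeats this for the co-primary endpoints.

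The per-arm interval reaches sparse cells by cross-reference:

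- SAP 6.3.1.1 gives the co-primary statistics for "Treatment group comparisons of the percentage of participants with pain freedom at each time point from 15 minutes through 48 hours postdose".
- SAP 6.2.17 and 6.3.4.1 do the same for return to normal function from 15 minutes.
- SAP 6.4 covers subgroups of the co-primary and key secondary endpoints: "Main analysis method described in Section 5.2.2 will be used, except for the subgroup analysis by country/region at randomization". They include BMI of 30 or more, prophylaxis use, aura before dosing and, for MBS freedom, each MBS type.

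Neither document gives an exact or score-based fallback, a minimum count, a rule for zero responders, or a statement on truncating limits at zero.

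**The concern.** The normal-approximation (Wald) interval takes its width from the observed proportion. Near zero the estimated variance shrinks with the estimate, so the interval is narrowest when the data say least about the upper limit. Rates of complete response 15 minutes after dosing may be very low, and some subgroups may be small.

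Time to onset is part of the stated study purpose, and version 2 of the SAP added subset analyses for the co-primary and key secondary endpoints. Readers will see these per-arm intervals in tables of early response and subgroup consistency. An interval labelled 95% that shows no uncertainty, or extends below zero, is wrong on its face and is likely to draw queries in a study report.

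**Working it through.** **Inputs from the documents.** Protocol 9.5 anticipates 90% of 700 per arm, "resulting in approximately 630 participants evaluable for efficacy in each treatment group". Its planning rates (zavegepant and placebo) are "23.2% and 15.1%, respectively, for pain freedom at 2 hours postdose" and "40.5% and 32.1%, respectively, for MBS freedom at 2 hours postdose".

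**Inputs assumed.** True early rates of 0.2% to 2%, and subgroup sizes of 15 to 100 per arm.

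**Plan's own figures.** The documents state no coverage. As a check on the inputs, a two-proportion power calculation at 630 per arm, two-sided 0.05, unpooled variance, gives 95.7% and 87.5%. These match Protocol 9.5. The product is 83.7%, against the stated 84% or so.

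**Formulas.** With x responders among n, p̂ = x/n and z = 1.96:

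- Wald: p̂ ± z√(p̂(1−p̂)/n).
- Wilson: [p̂ + z²/(2n) ± z√(p̂(1−p̂)/n + z²/(4n²))] / (1 + z²/n).
- Exact coverage at true rate p: the sum of the binomial probabilities of all x whose interval contains p.

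**Step 1: what happens at low counts (no assumed rate needed).**

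| Responders | Wald 95% CI | Wilson 95% CI |
|---|---|---|
| 0/630 | 0 to 0 | 0 to 0.61% |
| 1/630 | −0.15% to 0.47% | 0.03% to 0.89% |
| 2/630 | −0.12% to 0.76% | 0.09% to 1.15% |
| 3/630 | −0.06% to 1.01% | 0.16% to 1.39% |
| 0/20 | 0 to 0 | 0 to 16.1% |

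**Step 2: why coverage drops.** Take n = 630 and p = 0.2%. The chance of no responders is 0.998^630 = 28.3%, and the interval 0 to 0 then misses. The loss in the upper tail is under 0.1 point, so coverage is 71.6%. At p = 0.5%, x = 0 (4.3%) misses. So does x = 1 (630 × 0.005 × 0.995^629 = 13.5%), because its upper limit is 0.47%. The upper tail adds about 0.5%, so coverage is 81.8%.

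**Step 3: single-arm coverage.**

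| n per arm | True rate | Wald | Wilson |
|---|---|---|---|
| 630 | 0.2% (assumed) | 71.6% | 96.1% |
| 630 | 0.5% (assumed) | 81.8% | 95.9% |
| 630 | 1% (assumed) | 94.6% | 96.0% |
| 630 | 2% (assumed) | 92.6% | 95.5% |
| 100 (assumed) | 2% (assumed) | 86.6% | 94.9% |
| 15–39, mean (assumed) | 15.1% | 90.2% | 95.5% |
| 15–39, mean (assumed) | 23.2% | 91.8% | 95.3% |
| 630 | 15.1% to 40.5% (four planning rates) | 94.5%–95.3% | 94.7%–95.0% |

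Small-n coverage oscillates, so averages are more informative than one sample size. At n = 20 Wald gives 82.1% (15.1%) and 86.8% (23.2%). At n = 19 it gives 93.8% and 93.7%.

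**Step 4: treatment differences.** Exact coverage of the unstratified Wald difference, equal arms:

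| n per arm | Rates | Coverage |
|---|---|---|
| 630 | 0.5% v 0.2% | 94.7% |
| 630 | 1% v 0.5% | 94.5% |
| 20 | 23.2% v 15.1% | 93.6% |
| 20 | 40.5% v 32.1% | 94.2% |
| 50 | 5% v 2% | 91.4% |
| 30 | 8% v 4% | 90.2% |
| 20 | 5% v 2% | 75.6% |

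The difference falls clearly short only when small cells and rates of a few percent occur together. These figures do not test the stratified Mantel-Haenszel interval itself.

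**The case against.** The strongest reply is that nothing of consequence rests on these intervals. Testing follows p-values in a fixed sequence (SAP 5.1), and results for other secondary and exploratory endpoints are descriptive. The count and denominator are printed beside each interval, so 0/630 is visible. Early onset and subgroup consistency should be judged from the treatment difference. All of that stands, and it is why the point is minor.

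The low coverage figures rest on assumed rates and sizes. That also stands: no planned cell is shown to be that sparse. At 630 per arm Wald coverage is 94.6% at a true rate of 1%, although it dips again at other rates (90.3% at 1.5%).

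A reader might infer that the plan's early-onset and subgroup comparisons have only 70% to 87% coverage. The documents do not support this. Those values belong to single-arm intervals under chosen inputs, and Step 4 shows most differences near nominal. Nor does country stratification thin out the per-arm cells, since SAP 5.2.2 stratifies only the difference.

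What the reply does not answer is Step 1. A zero-width or partly negative 95% interval follows from the prescribed formula, and the SAP does not say what to do with it.

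**Conclusion.** The per-arm interval is wrong as written for sparse cells, and the consequence is minor. The 0 to 0 interval and the negative lower limits follow directly from SAP 5.2.2. The size of the coverage shortfall is conditional: about 72% to 82% at 630 per arm if true rates are 0.2% to 0.5%, about 87% at 100 per arm with 2%, and about 90% to 92% on average for 15 to 39 per arm at the protocol's pain-freedom rates. These are illustrations, not bounds or predictions. The co-primary per-arm intervals, the hypothesis tests and the gatekeeping are not affected.

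**What to change.** In SAP 5.2.2, replace the per-arm normal-approximation CI with the Wilson score interval for every per-arm rate in every table. Keep the Mantel-Haenszel difference, its standard error, CI and p-value as planned. Changing the difference interval as well could set it at odds with the p-value printed beside it, for little gain.

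Apply the change everywhere, not only in exploratory tables. The time course in SAP 6.3 includes 2 hours, so a partial change would put two different CIs on the same co-primary rate. Normal function at 15 minutes (6.2.17 and 6.3.4) would have the same problem. The co-primary tables barely move: at 95/630 (15.1%), Wald gives 12.3% to 17.9% and Wilson 12.5% to 18.1%.

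The cost is one sentence and a standard software option. There are two downsides. The per-arm CI is no longer the estimate plus or minus 1.96 ASE, so the table footnote should name the method. It also departs from the wording of Protocol 9.3.1 and 9.3.2.1, which should be recorded in SAP 2.1, now marked as not applicable. Protocol section 9 lets the SAP modify the outline and asks for an amendment only for major changes to the primary endpoints or their analyses. A descriptive per-arm interval does not appear to be one.

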### 5.2.3. Time-to-Event Analysis

Time-to-event distribution of endpoints (rescue medication use, pain freedom, MBS freedom, pain relief, normal function, phonophobia absence, photophobia absence, nausea absence) will be tabulated and plotted. Participants are considered to have an event through X hours ( $X=24$  hours or 8 hours) if the first post dose eDiary date/time defining a response is (1) at or before the upper bound of the X-hour analysis window in minutes (see Section 5.2.5), and (2) is before the imputed rescue medication start date/time, if not missing. Otherwise, participants who do not have an event through X hours are censored at the earliest of the following: (1) upper bound of the X-hour analysis window + 1 minute; (2) the imputed first rescue medication start date/time; (3) the last non-missing contact date/time.

For time to rescue medication use through 24 hours, participants are considered to have an event if the date/time of taking the rescue medication is prior to or at 24 hours post dose; otherwise, the time to rescue medication will be considered as censored at the earliest of the following: (1) 24 hours post dose + 1 minute, (2) the last non-missing contact date/time. For time to rescue medication use through 24 hours, the summary table and Kaplan-Meier plot will be using 2-hour time intervals: 0 to <2,  $\geq 2$  to <4,  $\geq 4$  to <6, ...,  $\geq 24$ . For exploratory endpoints through 8 hours, the summary table and Kaplan-Meier plot will be using the following time intervals: 0 to <15,  $\geq 15$  to <30,  $\geq 30$  to <45,  $\geq 45$  to <60,  $\geq 60$  to <90,  $\geq 90$  to <120,  $\geq 120$  to <180,  $\geq 180$  to <240,  $\geq 240$  to <360,  $\geq 360$  to <495, and  $\geq 495$  minutes.

The summary table will include the following statistics: number of participants at risk, number of participants with events, number of participants censored for each time interval; overall number and percentage of participants with events and censored; time-to-event estimate for median, first quartile, and third quartile with corresponding 95% CIs. The 95% CI will be estimated using the method of Brookmeyer and Crowley. The log-rank p-value will also be presented for comparison of zavegepant versus placebo. In the Kaplan-Meier plot, the percentage of participants for the endpoints within the time period postdose on the y-axis versus time in minutes on the x-axis will be displayed.

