## Overall Design:

This is a Phase 3, randomized, double-blind, placebo-controlled, multicenter, single-attack, outpatient evaluation of the efficacy and safety of zavegepant versus placebo for the acute treatment of migraine in Asian adults.

The total duration of study participation will be up to approximately 16 weeks. This includes a 3-28 day Screening Phase, a Treatment Phase that can last up to 45 days or until the participant has a migraine headache that reaches moderate or severe pain intensity, followed by an EOT Visit 7 (+2) days after the administration of study intervention, and a Follow-Up Visit 28-35 days after the administration of study intervention for safety monitoring. The study intervention will be zavegepant 10 mg or matching placebo. The study will randomize approximately 1400 participants in a 1:1 ratio between the 2 treatment groups (zavegepant or placebo). Randomization will be stratified by the use of stable prophylactic migraine medications through randomization (yes or no) and country/region.

After randomization, the participants will be dispensed a single dose of double-blind study intervention. The participants will be instructed to take study intervention as an outpatient, if they have a migraine headache of moderate or severe pain intensity, and only after they have reported their pre-dosing migraine characteristics in the eCOA handheld device. After

participants confirm taking study intervention in the eCOA handheld device, they will report the following efficacy data in the eCOA handheld device at 15, 30, 45, 60 and 90 minutes postdose, and 2, 3, 4, 6, 8, 24 and 48 hours postdose: headache pain intensity using a 4-point numeric rating scale (none, mild, moderate, severe); the status (present or absent) and intensity (mild, moderate, or severe) of migraine associated symptoms (nausea, photophobia, phonophobia), and their current MBS before taking study intervention; functional disability level using a 4-point numeric rating scale (normal, mildly impaired, severely impaired, requires bedrest). Participants will also complete the PGIC ratings at 30 minutes, 60 minutes, 2 hours and 24 hours postdose in the eCOA handheld device.

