### **6.9.2. Rescue Medication**

The study site will not supply rescue medication that will be obtained locally by participants. The date and time of rescue medication administration as well as the name and dosage regimen of the rescue medication must be recorded.

In all circumstances, the participant will always continue to complete the handheld entries through the 48-hour assessment after taking the study intervention. A Rescue Medication paper diary will be provided to participants at the Baseline Visit. Participants will record any rescue medication taken on the Rescue Medication paper diary and return to the site at the EOT Visit.

After administration of study intervention, **ALL other headache medication** is prohibited during the first 2 hours postdose of study intervention administration. A participant who does not experience relief of their migraine headache at the end of 2 hours after administration of study intervention (***and after the 2-hour assessments have been completed on the handheld device***), will be permitted to use ONLY the following rescue medication: ***aspirin, ibuprofen, acetaminophen up to 1000 mg/day (this includes Excedrin Migraine), naproxen (or any other type of NSAID), antiemetics (ie, metoclopramide or promethazine), or baclofen. These are the only medications allowed for rescue treatment after 2 hours postdose of study intervention.***

If the migraine is relieved by study intervention at 2 hours postdose but then returns to a moderate or severe pain intensity level between 2 and 48 hours postdose, the participant will be permitted to take the same rescue therapy as outlined above.

During the 45 days of the Treatment Phase, if the participant has a nonqualifying migraine (attack with mild pain) or a migraine that they do not treat with study intervention, the participant is permitted to use only the following medications: ***aspirin, ibuprofen, naproxen (or any other type of NSAID), antiemetics (ie, metoclopramide or promethazine), or baclofen.***

After completing all assessments in their handheld (through 48 hours postdose and before returning to the clinical site for EOT Visit), if participants experience a migraine, they are allowed to take their prescribed standard of care medication per local practice (including triptans if not contraindicated and acetaminophen up to 1000 mg/day, this includes Excedrin Migraine or other similar combination products), provided the medication is not otherwise prohibited.

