- Intercurrent event(s): Taking rescue medication at or before the corresponding assessed time points as specified in the endpoints postdose will be regarded as a failure.
- Population-level summary: Difference in percentage of participants achieving the specific outcome at time points of interest between zavegepant and placebo groups.

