##### 6.3.1.2. Supportive Analysis

Time to pain freedom through 8 hours postdose distribution will be presented, separately. Kaplan-Meier plot will also be displayed (see [Section 5.2.3](#) for details).

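### SAP 5.2.3 censors at first rescue in the seven time-to-response analyses, so the Kaplan-Meier curves and medians overstate response without rescue and depart from the rescue-as-failure estimand

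*SAP*

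**What the plan says.** SAP 5.2.3 sets one rule for time to pain freedom, MBS freedom, pain relief, normal function and absence of each of the three symptoms. A response is an event only if it falls inside the window and comes before rescue. Everyone else is censored at the earliest of "upper bound of the X-hour analysis window + 1 minute; (2) the imputed first rescue medication start date/time; (3) the last non-missing contact date/time". The output is a Kaplan-Meier plot whose y-axis is described as the percentage of participants with the endpoint, a table with the median, the quartiles and the overall count and percentage with events, and a log-rank p-value. Time to rescue has its own rule, with rescue as the event, and is not at issue.

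SAP 6.3.1.2 to 6.3.7.2 call up these analyses; the first reads "Time to pain freedom through 8 hours postdose distribution will be presented". The exploratory estimand for the same endpoints, SAP 2.2.3, is composite: "Taking rescue medication at or before the corresponding assessed time points as specified in the endpoints postdose will be regarded as a failure". Appendix 2.1.1 repeats rescue-as-failure for each endpoint. Appendix 1 labels the time-to-event rows as supportive and as using observed data, without naming another estimand.

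Protocol 6.9.2 bars other headache medication in the first 2 hours. After that it allows rescue to "A participant who does not experience relief of their migraine headache at the end of 2 hours", or to someone whose relieved attack returns to moderate or severe pain.

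**The concern.** Censoring at rescue makes Kaplan-Meier treat a participant who took rescue as someone who could still respond at the same rate as those left in the risk set. Under the composite strategy that participant has already failed. Under the protocol, rescue is taken because the attack is unrelieved or has come back, so those removed are not a random sample of those still at risk.

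Two consequences follow. First, the curve no longer shows what its axis says, and it can disagree with the event percentage in the same table, which does respect rescue as failure. A median can be printed that fewer than half of the arm reached. Second, the log-rank p-value answers a different question from the estimand. These outputs serve the stated objective of describing the time course of efficacy, so they are likely to be read at face value.

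**Working it through.** **Plan's own figures.** SAP 5.2.3 states no figure. As a check on the inputs borrowed from Protocol 9.5 (630 per group; 2-hour pain freedom 23.2% and 15.1%; MBS freedom 40.5% and 32.1%; 2-sided 0.05), power = Φ{[|p1 − p2| − 1.96·√(2·p̄(1 − p̄)/n)] / √[(p1(1 − p1) + p2(1 − p2))/n]}.
- Pain freedom: (0.081 − 0.0435)/0.0221 = 1.70, power 95.6% (stated 95.7%).
- MBS freedom: (0.084 − 0.0531)/0.0270 = 1.14, power 87.4% (stated 87.5%).
- Joint, as the product: 83.5% (stated 84%).

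**Direction of the error.** At each response time, cumulative incidence adds (fraction with neither response nor rescue so far) × (responders/at risk). One minus Kaplan-Meier adds (response-only survivor) × (the same ratio). The second multiplier is never smaller than the first, so 1−KM is at least as large as the proportion responding without rescue, whether or not rescue is related to response.

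**Size.** Assumptions, because the documents give neither rescue rates nor response rates after 2 hours: response by 2 hours p = 23.2% (zavegepant) and 15.1% (placebo); no rescue before 2 hours; constant hourly hazards λ (response) and μ (rescue) from 2 h to 8 h 15 min, that is 6.25 h. With S = 1 − p:
- 1−KM = 1 − S·exp(−6.25λ)
- response without rescue = p + S·[λ/(λ+μ)]·[1 − exp(−6.25(λ+μ))]
- rescue = S·[μ/(λ+μ)]·[1 − exp(−6.25(λ+μ))], solved for μ.

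Worked case, λ = 0.10 in both arms, rescue 15% (zavegepant) and 30% (placebo):
- 1−KM: 1 − 0.768 × 0.535 = 58.9%; 1 − 0.849 × 0.535 = 54.6%. Difference 4.3 points.
- Zavegepant, μ = 0.048: 0.232 + 0.768 × 0.676 × 0.603 = 54.5%. Placebo, μ = 0.099: 0.151 + 0.849 × 0.503 × 0.711 = 45.5%. Difference 9.0 points.
- Placebo median on the censored curve: 2 + ln(0.849/0.5)/0.10 = 7.3 h, although 45.5% respond. On the diary schedule it would appear at the 8-hour assessment, because the curve at 6 h is still 1 − 0.849·exp(−0.4) = 43.1%.

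Range (zavegepant / placebo, %; last digits may differ by rounding):

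| λ per hour | Rescue | 1−KM | Response without rescue | Overstatement, points |
|---|---|---|---|---|
| 0.10 / 0.10 | 5 / 5 | 58.9 / 54.6 | 57.5 / 53.1 | 1.4 / 1.4 |
| 0.10 / 0.10 | 20 / 20 | 58.9 / 54.6 | 53.0 / 48.7 | 5.9 / 5.9 |
| 0.15 / 0.10 | 20 / 20 | 69.9 / 54.6 | 61.6 / 48.7 | 8.4 / 5.9 |
| 0.10 / 0.10 | 15 / 30 | 58.9 / 54.6 | 54.5 / 45.5 | 4.4 / 9.1 |
| 0.20 / 0.15 | 20 / 35 | 78.0 / 66.8 | 67.5 / 51.5 | 10.5 / 15.3 |
| 0.20 / 0.15 | 30 / 15 | 78.0 / 66.8 | 61.7 / 60.6 | 16.3 / 6.2 |

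**Log-rank.** Simulation, 630 per arm, 1,500 runs, response read at the scheduled assessments; rejection under the SAP rule against rescue-takers held as non-responders to 496 min.
- Identical arms: 4.3% against 5.1%.
- Same response in both arms (15.1% at 2 h, then λ = 0.10), rescue 12% / 30%: 5.7% against 47.5%. Responder proportions do differ here, 49.7% and 43.4%.
- 23.2% / 15.1% at 2 h, λ = 0.12 / 0.10, rescue 13% / 30%: 95.3% against 99.9%.
- Second case, with the participants prone to rescue also made less likely to respond: SAP rule 20.4%, mean Z −1.07, in favour of placebo.

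The simulation standard error at 5% is √(0.05 × 0.95/1500) = 0.6 points.

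**The case against.** The strongest defence is that the plan intends something different here. The composite estimand is written for percentages at fixed time points, the main exploratory analyses estimate exactly that, and Appendix 1 gives the time-to-event rows a separate label. Part of this stands: rescue as failure is kept in the event definition and in the printed event percentage. But an observed-data label is not an estimand, and nothing in the SAP says the curve targets what would happen if rescue were unavailable.

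The limits of scope also stand. The analyses are supportive, their p-values are descriptive under SAP 5.1, and compliant participants take no rescue before 2 hours, so the early part of each curve is untouched.

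Three stronger readings are tempting, and the documents do not support them:
- A reader might infer that placebo is inflated more, so that the treatment difference is understated. That needs clearly higher rescue on placebo, and no rescue rates by arm are given. With equal rescue the inflation is equal, or larger on zavegepant if its response hazard is higher.
- A reader might infer that the log-rank test is biased outright. Under independent censoring it is a valid test of the cause-specific response hazard and holds its size. It becomes distorted when those prone to rescue are also less likely to respond. Protocol 6.9.2 makes that plausible but does not quantify it.
- A reader might expect the fix to make the curves match the response-by-time tables. It will not do so fully: the tables score status at each time point with missing data as failure, while the curve scores first response.

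**Conclusion.** The censoring rule is wrong as written for these seven analyses. It conflicts with the only estimand stated for the endpoints, and 1−KM, the median and the quartiles overstate response without rescue in every arm with rescue. The direction is algebraic. The size, about 1 to 16 points for assumed rescue of 5% to 35%, rests on assumed rescue rates and assumed constant hazards after 2 hours. The effect on the treatment difference can go either way. The log-rank test targets a different hypothesis from the estimand, and its behaviour depends on how closely rescue tracks non-response. The co-primary and key secondary analyses score rescue as failure directly and are unaffected, so the trial's confirmatory conclusions do not depend on this clause.

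**What to change.** In SAP 5.2.3, for every endpoint except time to rescue, keep the condition that a response must precede rescue and delete item (2) from the censoring list. State that a participant who takes rescue before responding stays in the risk set as a non-responder to the 8-hour upper bound plus 1 minute (8 h 15 min = 495; 495 + 1 = 496 minutes), whatever the date of later contact. Equivalently, treat rescue as a competing event, plot cumulative incidence and use a Gray-type test in place of the log-rank. If the sponsor wants to keep the censored version, it should name the hypothetical or while-not-rescued estimand that it targets and relabel the axis. Add a note that the curves show first response and so will still differ somewhat from the status-at-time-point tables.

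The cost is one clause and a line of derivation code. No new data are needed, because rescue times are already collected. The downside is that response estimates become lower and medians later, or not estimable where fewer than half respond.
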